Joint Health Study

November 9, 2016

Joint Health Study

Background

Hemophilia B is a congenital bleeding disorder caused by a mutation in the factor IX gene, resulting in low circulating clotting factor levels which has been associated with trauma induced and spontaneous bleeding into the joint space. Recurrent bleeding leads to risk for re-bleeding, hypertrophy of the synovium, progressive cartilage destructions and bony changes, resulting in hemophilic arthropathy, chronic pain and functional disability [Forsyth 2012]. Prophylactic treatment with clotting factor concentrates to prevent bleeding has been shown to reduce the risk for joint arthropathy [Manco-Johnson 2007] and has become standard of care.

Current prophylactic regimens, although very effective, do not completely prevent joint disease in a long-term perspective. Joint arthropathy in primary prophylaxis develops over many years, sometimes over a decade or even longer time periods. The ankle joints are the first and most severely affected joints in those patients and thus may serve in outcome assessment as an indicator of early joint arthropathy when followed by ultrasound or magnetic resonance imaging [Oldenburg, 2015].

[figure not shown]

Figure 1. Development of ankle arthropathy in a cohort on intensive lifelong prophylaxis, GS, Gilbert score; PS, Pettersson score [Oldenburg, 2015].

Screening for hemophilic arthropathy is generally conducted during annual comprehensive visits in hemophilia treatment centers, and several tools have been developed to assess for and monitor progression of arthropathy. The Gilbert Score and the Hemophilia Joint Health Score (HJHS) are clinical scores. The World Federation of Hemophilia Pettersson score and Arnold-Hilgartner score are based on x-ray findings and tend to reflect later, irreversible bony damage. Magnetic resonance Imaging (MRI) is sensitive to soft tissue changes and detects pathologic findings such as effusions, synovial hypertrophy, hemosiderin deposition, and

osteochondral changes. Numerous scales have been developed over the years (Denver score is a progressive score, European score is an additive score, Compatible score is a combined Denver and European score, IPSG score is currently the standard). While more sensitive for soft tissue changes, MRI is costly, not-easily assessable, takes a significant time commitment and necessitates sedation in children. Thus MRI is difficult to incorporate in the assessment of acute/bleeding and chronically changing joint.

More recently, musculoskeletal ultrasound (MSKUS) has been used for diagnosis of joint disease in hemophilia. Like MRI, it can reveal joint effusion, proliferation of synovium and subtle cartilage and bone abnormalities. It is the imaging modality recommended by the American College of Rheumatology and is superior to physical exam, especially when evaluating synovitis [Foltz 2012, McAlindon 2012, Porta 2012]. It has been demonstrated that ultrasound helps in the correct and timely diagnosis of acute bleeding episodes [Ceponis 2013], along with other musculoskeletal changes in people with hemophilia [Kidder 2015]. Advantages of MSKUS are its wide availability and low cost. Ultrasound will allow more thorough longitudinal joint assessment [Aznar JA 2015], assisting in the prevention of disease progression, thereby potentially improving outcomes and decreasing cost. Soft-tissue changes such as synovial hypertrophy, which precede joint disease, especially can be effectively diagnosed. Standardized and simplified ultrasound scanning protocols for early arthropathy detection in ankles, knees, and elbows have been published [Martinoli 2013]

Research Question

Knowledge pertaining to the progression of hemophilic arthropathy of patients with Hemophilia B is limited since Hemophilia B is very rare. Only 1 in 25,000 live male birth is affected compared to patients with Hemophilia A, born at a ratio of 1:5000 male birth (ref). To date, and to the best of our knowledge, there are no prospective studies available to document the development of hemophilia arthropathy in patients with Hemophilia B. We therefore propose to study longitudinal joint changes in patients with moderate and severe Hemophilia B. Most patients are on episodic or prophylactic FIX replacement therapy, whereby patients have a choice to be treated with newer extended half-life (EHL) products or to remain on traditional short-acting FIX products. For example, recombinant FIX albumin fusion protein (rIX-FP) is the most recently approved EHL concentrate and has demonstrated an increase in circulating half-life and area of the curve (AUC) of greater than fourfold versus unmodified FIX. When infused weekly this kinetic profile allows for potential trough levels of greater than 10% [Santagostino 2016]. Such improvement in minimum trough levels could improve the incomplete protection observed with previous products. This study will test the hypothesis that an EHL FIX product (such as rIX-FP) could offer better protection than previous treatment concentrates. The primary research question is whether EHL-rIX with an intended trough level of >5% will improve the outcome of joint health of elbow, ankle and knee joints as assessed with ultrasound assessment in severe hemophilia B patients.

Study Design

Prospective, non-randomized controlled study, whereby patients will be included in 1 of 3 groups depending on their current treatments as outlined below. Patients will be assigned to a specific group by the clinician/PI based on their current regimen with the intent to stay on this regimen for the next 3 years.

- Group A - episodic treatment with FIX concentrates for bleeding episodes
- Group B - prophylaxis using any FIX concentrate with an intended trough of 1-5%
- Group C – prophylaxis with an extended half-life FIX with an intended trough of > 10%

[figure not shown]
Primary Outcome

Joint health status in all 3 groups as assessed by MSKUS at 3 years.

Joint health will be assessed in all 6 major joints (elbows, knees and ankles), if possible, but at a minimum, target joints and the contra lateral joint will be included. During the exam the previously described Martinoli transducer positions will be used [Martinoli 2013]. To verify MSKUS, the first 10 patients will have parallel x-rays and MRI of the target joint and contra lateral joint.

Allocation of a comparison score of the MSKUS at baseline vs. year 3 will be done by a central, blinded person once all MSKUS images are available. The Joint Activity and Damage Exam (JADE) protocol will be documented to inform scoring. The scoring will be as follows:

MSKUS Assessment	Score
MSKUS imaging indicated improved joint status (decreased signs of arthropathy)	-1
MSKUS imaging indicated no change in joint status	0
MSKUS imaging indicated worsened joint status (increased signs of arthropathy)	+1

Secondary outcomes

- Observational assessment of joint and overall health status evaluated by activity level, functional assessment, pain assessment, joint examination, and adherence.
- Observational assessment of joint health at 1 and 2 years in the different groups
- Observational assessment of MSKUS findings during acute events/bleeding with an opportunity to follow longitudinally to gain understanding of natural evolution of bleeding on MSKUS
- Exploration of potential biomarkers for joint health

Patient Population

Inclusion Criteria

- Male gender
- Severe hemophilia B (factor IX < 1%)
- Age \geq 16 year
- Either on demand or on prophylaxis with rFIX or EHL-rIX products with the intention to stay on the current regimen for the next 3 years
- For Group C start of this treatment regimen up to 6 months ago is permissible
- Willing and able to give written informed consent/assent
- Willing to undergo MSKUS and /or collection of blood sampling for biomarkers

Exclusion Criteria

- Other known bleeding disorder
- Other rheumatologic disorder affecting joints
- Other known neuromotor defect (making physical exam difficult)

Assessment at baseline and at annual exams: Patients will be consented and eligibility will be confirmed. The following will be collected:

- Baseline Form (Demographics, bleeding history, use of hemostatic agents, past medical/surgical history, vital signs)
- Rapid Assessment of Physical Function (RAPA – 1 page questionnaire) to assess physical activity level
- Hemophilia Activity List (HAL – 3 page self –administered questionnaire) and Time up and go (TUG – assessed by PT) to assess function
- VERITAS-Pro (24 question self-administered questionnaire) for Arm B and C to assess adherence to prophylaxis
- Brief Pain Inventory (BPI – 10 question self-administered questionnaire)
- Joint Assessment (Hemophilia Joint Health Score =HJHS)
- MSKUS: Full J.A.D.E. Protocol (prior exams up to 3 months are permissible)
- x-rays and MRI (first 10 patient only prior exams up to 3 months are permissible)
- Treatment Plan prescribed at visit
- Labs: Factor XI level, FXI inhibitor, hsCPR
- Plasma Sample for biomarkers for Bio Repository

Historical assessments up to 1 year will be allowed as long as all required data was collected.

Assessment of painful episodes: Patients participating in this study will be encouraged to come in for an assessment during a painful episode of either of their elbows, knees or ankles. They will be asked to classify the episode as a bleed vs. non-bleed. The pertinent joint will be examined by a healthcare practitioner as classified to be a bleed vs. non-bleed by the practitioner and a treatment will be determined according to the exam. The patient then will undergo MSKUS and the treatment plan will be reviewed. If changes are made based on the MSKUS findings, they will be noted. The patient is offered to have a sample for the biomarker repository drawn.

Assessment post-painful episodes: Patients who came in for a painful episode are encouraged to return to clinic in 1-2 weeks for repeat exam and MSKUS. The patient is offered to have a sample for the biomarker repository drawn.

Assessment Schedule:

	Baseline	Acute Pain Event	Post-Pain Event	Year 1,2	Year 3
Demographics (age, race/ethnicity)	X			X	X
History (including bleeding history, medications, hemostatic agents and regimen, surgeries, joint bleeding/injury/surgery)	X	X	X	X	X

Recent joint bleeding/injury history (over the last 1 year)	X			X	X
Activity level (e.g RAPA or fitbit)	X	X	X	X	X
Functional assessment (HAL)	X	X	X	X	X
Brief Pain Inventory	X	X	X	X	X
Physical Exam	X	X	X	X	X
HJHS	X	X	X	X	X
MSKU	X	X	X	X	X
Biomarkers	X	X	X	X	X
X-ray (1 st 10 patients only)	X			X*	
MRI (1 st 10 patients only)	X			X*	
Time to up and go	X	X (if appropriate)	X (if appropriate)	X	X
Veritas or Veritas-Pro - Adherence	X	X	X	X	X

*Year 1 only

MSKUS Assessment: MSKUS will be performed by a qualified person at each study site. To reduce operator dependence of results and ascertain uniform data collection, this person must have had sufficient training (took a course on hemophilia related MSKUS though [name], through UCSD, or equivalent). Preferably, the MSKUS is performed by the same person at each time point. Assessment at each time point should be of bilateral elbows, knees and ankles, if possible – at a minimum, MSKUS of an acute or historical target joint (elbow, knee or ankle) and the contralateral joint has to be performed at baseline and at 3 years to be included in primary endpoint analysis.

X-ray Assessment: The 1st 10 patient in the study will have x-rays of their target joint and contralateral joint using the following views:

- Knee – radiographs: standard AP and lateral, but also include a merchant view (3 views total)
- Elbow – radiographs: standard AP and lateral (2 views)
- Ankle – radiographs: standard AP, lateral, and mortise (3 views)

x-ray studies done within 6 months of study visit are permissible.

MRI Assessment: The 1st 10 patient in the study will have MRI images of their target joint and contralateral joint using the following protocol:

Preferably imaging should occur on a 3 Tesla machine and each site will have their own standard clinical MRI protocols using conventional 2D sequences in 3 imaging planes (typically fast spin echo [FSE]). In addition, add a sagittal 2D gradient echo sequence (to better visualize hemosiderin deposits) and also a 3D sequence. The 3D sequences are depending on particular MRI vendor at the individual sites. If available a 3D FSE should be performed (GE has CUBE, Siemens has SPACE, Philips has VISTA, Hitachi has isoFSE, and Toshiba has 3D MVOX). Acquisition for the 3D sequence should be in the sagittal plane and voxel size should be close to isotropic. The 3D sequence will be very useful for comparing specific planes with ultrasound (such as the femoral trochlea). The radiology consultant for this study will advise on sequencing at each individual site.

MRI studies done within 6 months of study visit are permissible.

Biomarker Repository: During all visits, including acute pain and pain follow-up visits, the patient will be approached to contribute blood samples for the repository. Five citrated (blue top) tubes will be drawn, samples will be spun, aliquoted and frozen for potential later studies.

Cost to the patient: This study will cover the cost for the MSKUS performed, the x-ray and MRI validation exams for the first 10 patients. It will not cover the cost of the clotting factor and routine clinical laboratory.

Patient compensation: The patient will be compensated for his time for the baseline, year 1, year 2, year 3, acute pain episode and pain follow-up visit at \$150.-/visit. Patients are allowed to get evaluation for more than 1 pain episode and data can be included in the analysis, but there is no compensation for these additional visits. There will also be up to \$50.-/visit in travel compensation for the baseline, year 1, year 2, year 3, and one acute pain episode and pain follow-up visit.

Statistical Plan

For first 10 patients do MRI, compare Ultrasound to MRI and X-ray at baseline and 1 year; and compute sensitivity and specificity and evaluate the rate of false negatives by ultrasound, with MRI as gold standard.

The primary outcome will be proportion of patients with improvement (compared to same or worse) between groups B and C, with analysis by Fisher's Exact Test. Given a feasible sample size of 20 patients per arm for groups B and C, we anticipate having 80% power to detect a 5-fold increase in the proportion of patients classified as improved (e.g., from 10% to 50%). Proportions in each group classified as worse, same, or improved will also be reported and compared by Fisher's Exact Test.

Sample Size

- Arm A: 10 patients
- Arm B: 20 patients
- Arm C: 20 patients

Potential Study Sites

- Washington Center for Bleeding Disorders at Bloodworks NW, Seattle, WA
- Hemophilia and Thrombosis Treatment Center, University California, San Diego, CA
- Seattle Children's Hospital, Seattle, WA
- Orthopedic Hemophilia Treatment Center, Los Angeles, CA
- Tulane University, New Orleans, LA
- Hemophilia and Thrombosis Center, Denver, CO
- Center For Inherited Blood Disorders, Irvine, CA
- Children's Hospital of Michigan, Detroit, MI
- Oregon Health & Science University, Portland, OR

References

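### Groups B and C are formed by current regimen with no condition on the previous one, and the B vs C test ignores regimen history, so the effect of starting prophylaxis can mix with the effect of the higher-trough EHL regimen

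*Combined protocol and SAP*

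**What the plan says.** - **Allocation (Study Design).** The study is non-randomised: "Patients will be assigned to a specific group by the clinician/PI based on their current regimen". Group B is prophylaxis with any FIX concentrate at an intended trough of 1-5%. Group C is prophylaxis with an extended half-life FIX at an intended trough above 10%.
- **Eligibility (Inclusion Criteria).** For all groups: "Either on demand or on prophylaxis with rFIX or EHL-rIX products with the intention to stay on the current regimen for the next 3 years". A further criterion applies to one group alone and concerns when its regimen began: "For Group C start of this treatment regimen up to 6 months ago is permissible". Group B has no start window. No inclusion or exclusion criterion mentions the regimen before the current one.
- **Endpoint (Primary Outcome).** A central blinded reader compares the baseline and year-3 ultrasound and scores each patient as improved, unchanged or worse.
- **Analysis (Statistical Plan).** The primary comparison is the "proportion of patients with improvement (compared to same or worse) between groups B and C". Fisher's exact test is used, on 20 patients per group. No stratification, adjustment or restriction is planned.
- **Data collected (baseline assessments and Assessment Schedule).** History includes haemostatic agents and regimen. The previous regimen and the start date of the current one are not named as items, and the history has no role in the analysis.

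**The concern.** The endpoint is change from the enrolment scan, so a treatment change shortly before enrolment matters. A Group B patient on the same prophylaxis for years is scanned twice under unchanged treatment. A patient who has just left episodic treatment is scanned near the start of prophylaxis and again three years into it. Any improvement he shows may come from being on prophylaxis at all, which the Background already describes as reducing arthropathy risk and as standard of care.

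The research question is different: whether an EHL regimen with a higher trough protects joints better than other prophylaxis. If former episodic patients are more common in C than in B, C can do better with no trough or product effect, and the planned test cannot tell the two explanations apart. Adjusting for baseline joint status would not settle it, because two patients with the same baseline scan can differ in whether they have just started prophylaxis.

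**Working it through.** **1. The plan's own figure.** Inputs from the Statistical Plan: 20 per group, 10% vs 50% improved, 80% power. Significance level and sidedness are not stated; two-sided 0.05 is assumed throughout.

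Pooled normal approximation, with mean rate 0.30:
z = (0.40·√20 − 1.96·√(2·0.30·0.70)) / √(0.10·0.90 + 0.50·0.50) = (1.789 − 1.270) / 0.583 = 0.89, so power is 81.3%.

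The 80% is therefore reproduced. For the test the plan names, exact enumeration of Fisher's test over all 21 × 21 outcomes gives 74.2%. That gap is a separate matter; the enumeration is the tool used below.

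**2. What the design leaves open**

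| | Group B | Group C |
|---|---|---|
| Start of current regimen | no line | up to 6 months ago is allowed |
| Previous regimen | no condition | no condition |
| Role of either in the primary test | none | none |

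**3. Illustration with no trough or product effect.** Let s be the share of a group that recently moved from episodic treatment, and q the improvement rate among these starters. Everyone else improves at 10%, the lower rate in the plan's example. Then

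p = 0.10·(1 − s) + q·s,

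and the spurious difference between groups is (s in C − s in B)·(q − 0.10). The documents give neither s nor q, so both are assumptions shown as a range.

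No starters in B (B = 10%):

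| s in C | q | C improved | Spurious difference | Fisher significant |
|---|---|---|---|---|
| 0 | – | 10% | 0 points | 1.2% |
| 25% | 30% | 15% | 5 points | 2.9% |
| 50% | 30% | 20% | 10 points | 7.2% |
| 25% | 50% | 20% | 10 points | 7.2% |
| 50% | 50% | 30% | 20 points | 24.2% |

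**4. Starters in B as well.** Take s = 25% in B and q = 50%, so B = 0.10·0.75 + 0.50·0.25 = 20%.
- C also at s = 25% (20% improved): no spurious difference; significant in 2.3%.
- C at s = 50% (30% improved): 10 points; significant in 6.2%, against 24.2% with no starters in B.

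The distortion therefore depends on the imbalance in starters between the groups, not on their presence in C alone.

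**5. Cost of restricting.** Exact Fisher power for 10% vs 50% is 74.2% at 20 vs 20. If C falls to 10 patients, it is 62.8% with 20 in B and 51.5% with 15 in B.

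**The case against.** **A recent switch is not in itself a bias.** For a patient moved from 1-5% prophylaxis to >10%, the change is the intervention under study, and a baseline near its start is needed to observe its effect. A reader might infer that C can win simply because its patients have just changed treatment and B's have not. For switchers between prophylaxis regimens the documents do not support that: the Research Question itself contrasts newer EHL products with remaining on traditional ones. This objection stands, and it narrows the concern to patients arriving from episodic treatment.

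**The 6-month line may be only a permission.** A reader might infer that every Group C patient is a recent starter who has stepped up from something weaker. As an inclusion criterion that mentions no earlier start, the line can be read as a limit, but its wording only permits. If it is a permission, C mixes recent and established patients. On either reading a patient may have come from another EHL regimen. The objection stands; the ambiguity itself needs resolving.

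**The numbers are hypothetical.** Larger figures are easy to produce: with 75% of C from episodic treatment and a 50% starter rate, the test is significant in 49.2% of trials. Nothing in the documents supports such a share, and the Background's description of prophylaxis as standard of care speaks against it. The 50% rate is only the plan's example of a detectable effect. Starters in B also offset the distortion. All of this stands.

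**Confounding is expected in a non-randomised study, and the history is largely collected.** Both are true. But the Research Question says the study will test a hypothesis of better protection, and the Statistical Plan does not use the history.

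**Conclusion.** The concern holds in a limited form. Prior regimen is unrestricted, a start-time line exists for Group C only and is ambiguous, and the primary test uses neither item. An excess of recent movers from episodic treatment in C would therefore be credited to the trough or the EHL product.

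The size cannot be known from the documents. With 25-50% of C from episodic treatment, starter rates of 30-50%, 10% improved otherwise and no starters in B, a test that is significant in 1.2% of trials when the groups are alike becomes significant in about 3% to 24%. The upper end needs both the larger share and the larger rate, and starters in B bring it down. If the groups have equal shares of such patients, this distortion disappears; the opposite imbalance would favour B.

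This should be corrected because the remedy is cheap. It does not show that the B vs C comparison is invalid.

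**What to change.** 1. State whether the 6-month line is a limit or a permission, and whether any start window applies to Group B.
2. For every B and C patient, record the previous regimen (episodic, or prophylaxis with its intended trough) and the start date of the current regimen. Tabulate both by group.
3. Before the central year-3 scoring, pre-specify a B vs C analysis stratified by prior regimen (episodic vs prophylaxis).
4. Pre-specify a sensitivity analysis that excludes, **in both groups**, patients whose previous regimen was episodic and who started prophylaxis recently (for example within 6 months). The start date is needed here, because prior regimen alone puts a patient who left episodic treatment long ago in the same stratum as one who has just done so. Removing recent starters from B only would create a new asymmetry.
5. If the result does not hold in these analyses, report that the B vs C difference cannot be attributed to the trough or product alone.

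**Cost.** Two defined fields on the baseline form, largely drawn from history already taken, and two short analyses; no extra visits or patients. The drawback is imprecision: with about 20 per group, losing half of C lowers power for 10% vs 50% from 74% to between about 51% and 63%, depending on how many remain in B. A failure to reach significance there would not by itself refute the primary result, so estimates with confidence intervals should be compared. These analyses qualify the primary result and do not replace it.

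### Does the plan need a separate B versus C test of worsening, given that its hypothesis is better protection?

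*Combined protocol and SAP*

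**What the plan says.** All references are to the combined protocol and SAP.

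- **Research Question.** The hypothesis is that an extended half-life product "could offer better protection than previous treatment concentrates". The same paragraph then puts the primary question as whether such a product "will improve the outcome of joint health of elbow, ankle and knee joints as assessed with ultrasound assessment in severe hemophilia B patients".
- **Primary Outcome.** The outcome is "Joint health status in all 3 groups as assessed by MSKUS at 3 years". A blinded central assessor compares baseline with year 3 and scores each patient -1 (improved), 0 (no change) or +1 (worsened), so worsening has its own level.
- **Statistical Plan, primary test.** "The primary outcome will be proportion of patients with improvement (compared to same or worse) between groups B and C", by Fisher's exact test. The stated power of 80% concerns improvement only, with 10% v 50% as the example and 20 patients in each of B and C.
- **Statistical Plan, supporting comparison.** "Proportions in each group classified as worse, same, or improved will also be reported and compared by Fisher's Exact Test". The groups are not named. The natural reading is one test across the three categories, because a separate test of the improved proportion would only repeat the primary one.

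**The concern.** Protection ordinarily means fewer joints getting worse. The primary test pools stable patients with deteriorating ones, so a treatment that halts deterioration without reversing damage cannot make it positive. Worsening enters formal inference only through the three-category comparison, which responds equally to a difference in improvement. Because that comparison does not name its groups, it could also be run on A, B and C together and reject because of Group A alone.

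Two misreadings would follow. A negative primary result might be taken as evidence of no protection. A significant three-category result, printed beside a lower worsening rate in C, might be taken as protection when improvement or Group A produced it. With "Observational assessment of joint health at 1 and 2 years in the different groups" among the secondary outcomes, a worsening comparison named late could also look chosen after the fact.

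**Working it through.** **Inputs.** From the Statistical Plan: 20 patients in each of B and C, Fisher's exact test, 10% v 50% improved, 80% power. Assumed because the document is silent: two-sided 5%, no dropout, and every worsening rate.

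**The plan's own figure.** Pooled normal approximation with p1 = 0.10, p2 = 0.50, mean 0.30, n = 20:

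z = (0.40·√20 − 1.96·√(2·0.30·0.70)) / √(0.10·0.90 + 0.50·0.50) = (1.789 − 1.270) / 0.583 = 0.89, so power = 81.3%.

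This reproduces the stated 80%. Exact enumeration of the two-sided Fisher test gives 74.2%. That is a separate matter from the one examined here.

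**Method.** All pairs of (improved, same, worse) counts for B and C, 20 each, were listed and weighted by their multinomial probabilities. The three-category p-value is the total conditional probability of all tables with the same margins that are no more probable than the one observed. The primary test is the two-sided Fisher test on improved v not improved; the worsening test is the same on worse v not worse.

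**Case 1: only improvement differs (10% v 50%), worsening equal in B and C.**

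| Worsening in both | Three-category test rejects | Of those: C has fewer worsened | Of those: primary also significant | Three-category significant, primary not, fewer worsened in C (share of all trials) |
|---|---|---|---|---|
| 10% | 77.1% | 39% | 94% | 0.47% |
| 20% | 77.5% | 42% | 91% | 0.14% |
| 30% | 81.7% | 43% | 88% | 0.06% |

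The third column is what makes the concern look serious. The fourth shows that those rejections mostly come with a positive primary test, which tells the reader that improvement differs. The last column is the pattern that would mislead. With smaller improvement differences (10% v 20, 30 or 40%) and the same worsening rates, it stays at or below 1.5%.

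**Case 2: only worsening differs, improvement 10% in both.**

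| Worsened, B v C | Primary rejects | Three-category rejects | Worsening-only test rejects | Three-category significant, primary not, fewer worsened in C |
|---|---|---|---|---|
| 50% v 10% | 1.2% | 77% | 74% | 76% |
| 40% v 10% | 1.2% | 53% | 49% | 52% |
| 30% v 10% | 1.2% | 28% | 24% | 27% |

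At 20% v 10% the two supporting tests have 10% and 7% power, so neither would settle the question.

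**A single table.** Improved/same/worse of 2/14/4 in B and 10/8/2 in C gives a three-category p of 0.024 and a worsening p of 0.66, which alone looks like a trap. The primary test on the same data (2/20 v 10/20) gives p = 0.014, so the source of the difference is in plain view.

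**Group A.** If the supporting test were run on all three groups, with 10 patients in A, B and C identical at 20% worse, and A assumed at 50/60/70% worse, it would reject in 34/55/77%. The plan does not state a three-group test, and the group proportions it promises to report would show A as the outlier.

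**The case for a change.** The strongest case for a change is about attribution, not power. One three-category p-value can belong to opposite findings: 2/8/10 in B v 2/16/2 in C (C better), the reverse (C worse), and 2/16/2 v 10/8/2 (improvement only) all give p = 0.0099. No test named in the plan, on its natural reading, is confined to worsening. If improvement does differ, the planned tests cannot say whether worsening differs as well. A named B v C comparison of the proportion worsened would need no new data.

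The facts in this stand; the need for a change does not follow. The first two tables are told apart by the reported proportions, and the third by the primary test (p = 0.014, against 1.0 for the first two). A separate worsening test has slightly less power than the planned one for pure prevention and would be one more uncontrolled p-value. Its confidence interval would be wide: 4/20 v 2/20 worsened is a difference of 10 points with a 95% interval (Newcombe) of -13 to 33. Anyone can obtain that interval from the proportions the plan already commits to report.

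The unnamed groups are a real gap in wording, but a small one. The sentence follows directly on the B v C primary test, and analysts would name the groups when they report it.

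**Conclusion.** No change follows. The improvement endpoint is an explicit, powered choice that fits the primary research question as worded, even though the hypothesis sentence speaks of protection. That a negative primary result does not rule out protection is a caution for interpretation, not a fault in the analysis.

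Worsening is scored, reported by group and compared. Read with the primary test, the three-category result points wrongly towards less worsening in C in at most 1.5% of trials across the improvement-only scenarios examined. It points that way correctly in 76/52/27% when worsening is truly 50/40/30% v 10%. Naming B v C in the supporting sentence and reporting the difference in proportion worsened with its interval would be a harmless clarification; the planned analyses give no wrong result without it.

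This rests on a two-sided 5% level, full follow-up of 20 per arm, a supporting comparison made between B and C, and assumed worsening rates, since the document gives none. Small differences in worsening would go undetected with or without a separate test.
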